**Confidentiality Statement**

This document is the property of Worldwide Clinical Trials Inc. and may not be duplicated, copied, altered or removed from company without prior approval from Worldwide Quality Assurance or in compliance with Worldwide Standard Operating Procedures.

Worldwide Clinical Trials Controlled Quality Management Document			
 WORLDWIDE CLINICAL TRIALS	Sponsor:	EIP Pharma, Inc.	
	Protocol Number:	EIP21-NFD-504	
STATISTICAL ANALYSIS PLAN			

Listing Number	Listing Title	Validation Method	Shell Number (if repeat)	Topline
16.2.6.9	Movement Disorder Society – Unified Parkinson’s Disease Rating Scale Part III - mITT Analysis Set	IP		
16.2.7	Adverse Event Listings			
16.2.7.1	Adverse Events - Safety Analysis Set	IP		Topline
16.2.7.2	Adverse Events Leading to Early Withdrawal - Safety Analysis Set	IP	16.2.7.1	Topline
16.2.8	Individual Laboratory Measurements and Other Safety			
16.2.8.1	Hematology - Safety Analysis Set	IP		
16.2.8.2	Chemistry - Safety Analysis Set	IP		
16.2.8.3	Coagulation - Safety Analysis Set	IP		
16.2.8.4	Vital Signs - Safety Analysis Set	IP		
16.2.8.5	12-Lead Electrocardiogram at Screening - Safety Analysis Set	IP		
16.2.8.6	Physical Examination - Safety Analysis Set	IP		
16.2.8.7	Columbia-Suicide Severity Rating Scale - Safety Analysis Set	IP		
16.2.8.8	Pregnancy Test Data – Safety Analysis Set	IP		

## 11 APPENDIX A: TEST INFORMATION AND COGNITIVE DOMAIN ASSESSED

Endpoint	Cognitive Domain	Primary Outcome (Variable)	Interpretation	Range Values
Detection Test (DET)	Psychomotor Function	Speed of performance; mean of the log10 transformed reaction times for correct responses	Lower score = better performance	2.001 to 6
Identification Test (IDN)	Attention	Speed of performance; mean of the log10 transformed reaction times for correct responses	Lower score = better performance	2.001 to 6
One Card Learning Test (OCL)	Visual Learning	Accuracy of performance; arcsine square root proportion correct	Higher score = better performance	0 to 1.5708
One Back Test (ONB)	Working Memory	Speed of performance; mean of the log10 transformed reaction times for correct responses	Lower score = better performance	2.001 to 6
	Working Memory	Accuracy of performance; arcsine square root proportion correct (Additional outcome)	Higher score = better performance	0 to 1.5708
International Shopping List Test (ISLT)	Verbal Learning Tell me the items on the shopping list.	Number of correct responses remembering the word list on three consecutive trials	Higher score = better performance	0 to 999

QMD Ref: Worldwide-TMP-ST-054-1.0_Effective: 12Aug2022	Governing QMD: Worldwide-SOP-ST-026
Confidentiality Statement	
This document is the property of Worldwide Clinical Trials Inc. and may not be duplicated, copied, altered or removed from company without prior approval from Worldwide Quality Assurance or in compliance with Worldwide Standard Operating Procedures.	

Worldwide Clinical Trials Controlled Quality Management Document		
 Worldwide Clinical Trials	Sponsor:	EIP Pharma, Inc.
	Protocol Number:	EIP21-NFD-504
POST DATABASE LOCK STATISTICAL ANALYSIS PLAN ADDENDUM		

## 1. BACKGROUND

This document details changes and / or additions to the planned statistical analyses for EIP Pharma, Inc, Protocol “EIP21-NFD-504” study previously described in V3.0 of the Statistical Analysis Plan (SAP) dated 24-OCT-2024.

These amendments were made post database lock and after the study was unblinded.

Rationale for Addendum:

- 1) Removal of treatment\*time interaction term from the efficacy analysis model.
- 2) Definition added for missing last dose date.
- 3) Additional tables generated to report the efficacy analysis for subjects with pTau181 <21 pg/mL at Screening.

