## 5 PLANNED ANALYSES

The Statistical Analysis Plan (SAP) and Table, Figure, Listing (TFL) Shells (and any amendments) must be approved prior to breaking of the blind for the primary and secondary analysis. If post database lock, additional statistical analyses or changes to the statistical analysis are required, then those will be documented in a Post Database Lock Statistical Analysis Plan Addendum.

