#### 2.1.2 New Text

Section 2.3 Estimand

Analysis Approach:

The difference between treatment arms in the average change from Baseline of the CDR-SB score will be estimated from a linear mixed effects model, including treatment group, and time in weeks as fixed effects; stratification factors (with and without cholinesterase inhibitor therapy), sex and baseline value as covariates. The random effect is on the subject term.

### 2.2 Change 2

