## 2.2.2 New Text

### Section 5.10.2.1 Primary Analysis

The difference between neflamapimod and placebo in the average change from baseline in CDR-SB score during the double-blind treatment phase (i.e., utilizing data from week 8, 12 and 16 in the model) will be estimated using a linear mixed effects model including treatment, time (in weeks) as fixed effects, cholinesterase inhibitor therapy (Yes/No), age, sex and baseline value as covariates.

## 2.3 Change 3

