### 2.3.1 New Text

#### Section 5.10.2.1 Primary Analysis

##### Example SAS code:

```
proc mixed data=  method = REML alpha=0.05;
  class <subject> <treatment> <cholinesterase inhibitor therapy> <sex>;
  model <change from baseline> = <treatment> < cholinesterase inhibitor therapy> <sex> <age> <
  baseline value> <time in weeks> / ddfm=kr s;
  random <time in weeks> / subject=<subject> type=un;
  lsmeans <treatment> / cl diff;
run;
```

## 2.4 Change 4

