##### 3.1.1 New Text

###### 5.2.9.1 Missing Date of Last Dose of Study Drug

In case the last dose date is missing for a subject, the date of last scheduled visit completed will be used as last dose date.

#### 3.2 Addition 2

Following additional tables are added to the analysis

Table Number	Table Title	Validation Method	Shell Number (if repeat)
Items in bold are not table titles but references to the section headings within eCTD.			
14.2	Efficacy Data		
14.2.1	Primary Efficacy Endpoint		
14.2.1.1c	Primary Endpoint, Clinical Dementia Rating Scale-Sum of Boxes (Descriptive statistics), pTau181 <21 at Screening - Double-Blind Treatment Phase - mITT Analysis Set	Stat IPS	14.2.1.1a
14.2.1.2b	Primary Endpoint, Clinical Dementia Rating Scale-Sum of Boxes (Linear Mixed Effects	Stat IP	14.2.1.2

QMD Ref: Worldwide-TMP-ST-056-2.0_Effective: 12Aug2025	Governing QMD: Worldwide-SOP-ST-026
Confidentiality Statement This document is the property of Worldwide Clinical Trials Inc. and may not be duplicated, copied, altered, or removed from company without prior approval from Worldwide Quality Assurance or in compliance with Worldwide Quality Management Documents.	

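### The primary model was replaced after unblinding, with no reason given and no statement of which model's p-value opens the testing hierarchy

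*SAP*

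**What the plan says.** SAP V3.0, Sections 2.3 and 5.10.2.1, fixes a linear mixed effects model for CDR-SB change at Weeks 8, 12 and 16 with treatment, time in weeks and treatment-by-time. Section 5.10.2.2 uses the same model after multiple imputation. Sections 5.10.3.1 (TUG) and 5.10.3.2 (NTB) take their model from Section 5.10.2.1.

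The addendum's Background states: "These amendments were made post database lock and after the study was unblinded". Its first rationale item is removal of the treatment-by-time "interaction term from the efficacy analysis model". The replacement texts are:

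- Section 2.3: "including treatment group, and time in weeks as fixed effects".
- Section 5.10.2.1: "including treatment, time (in weeks) as fixed effects, cholinesterase inhibitor therapy (Yes/No), age, sex and baseline value as covariates".
- The example code for the primary and the sensitivity analysis: the model statement now ends "baseline value> <time in weeks> / ddfm=kr s".

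Section 5 says that the SAP, the shells and any amendments "must be approved prior to breaking of the blind for the primary and secondary analysis". For changes needed after lock it says "then those will be documented in a Post Database Lock Statistical Analysis Plan Addendum".

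Section 5.10.5 opens TUG only if the two-sided primary p-value is below 0.05, and opens NTB and ADCS-CGIC only after TUG. The addendum does not amend it. Addendum 3.2 begins "Following additional tables are added to the analysis", and every table listed there is for participants with screening pTau181 <21. Table 14.2.1.2 remains the only model table for the primary endpoint in the full mITT set.

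**The concern.** Three things combine.

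1. The model that yields the primary p-value was changed when treatment codes were known.
2. The rationale repeats the change and does not justify it. It cites no convergence failure, coding error or blinded decision.
3. The new model has no stated status. It is issued as replacement text for the primary analysis, yet nothing keeps V3.0 as confirmatory, labels the new model post hoc, or links either model to Section 5.10.5.

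The primary p-value admits or blocks the whole secondary hierarchy, so its model should be the one fixed before unblinding. The deletion can also change what is estimated. Section 2.3 targets the treatment difference in mean change over the double-blind phase. A model that assumes one common difference at all visits weights them by precision, which need not give that mean.

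**Working it through.** **Textual check.** Section 5 does two things: it requires approval before the blind is broken, and it requires later changes to be documented. It does not say that a documented post-lock model becomes confirmatory. Section 5.10.5 refers to the primary endpoint's p-value without naming a model. Two readings remain: the addendum model is now the gate, or the gate is undefined. Neither leaves the prespecified model clearly in charge.

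**What the plan gives.** Inputs are 80 per arm, 10% dropout, two-sided 0.05 (Sections 3 and 5.10.1), and visits at Weeks 8, 12 and 16 (Section 5.10.2.1). The reproducible power statement in Section 3 is for patients without AD co-pathology: a difference of 0.56 with d = 0.70 implies SD = 0.56/0.70 = 0.80. A two-sample calculation gives 99.3% power at 80 per arm and 98.7% at 72, consistent with the stated >95%. The plan gives no visit covariance and no effect shape, so those below are assumptions.

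**Visit weights, complete data.** Let V be the covariance of the three visit values, **1** a vector of ones and t = (8, 12, 16).

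- Addendum (common difference): w = V⁻¹**1** / (**1**′V⁻¹**1**).
- V3.0 (difference linear in time, LSMEANS at mean time 12): w is the first row of (X′V⁻¹X)⁻¹X′V⁻¹, with X = [**1**, t−12].

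The example code has a random slope on time and no intercept, so there V = I + k·tt′/144, where k is the slope variance at Week 12 divided by the residual variance. CS and AR are compound symmetric and autoregressive correlation.

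| Assumed V | V3.0 weights | Addendum weights |
|---|---|---|
| Random subject intercept | 0.33 each | 0.33 each |
| Unstructured, CS 0.6, equal SDs | 0.33 each | 0.33 each |
| Unstructured, AR 0.7, equal SDs | 0.43/0.13/0.43 | 0.43/0.13/0.43 |
| CS 0.6, SD 0.9/1.0/1.1 | 0.33/0.34/0.33 | 0.56/0.31/0.14 |
| CS 0.6, SD 0.8/1.0/1.2 | 0.33/0.34/0.33 | 0.77/0.24/-0.01 |
| CS 0.6, SD 1.2/1.0/0.8 | 0.33/0.34/0.33 | -0.01/0.24/0.77 |
| Slope-only code, k = 0.5 | 0.33 each | 0.48/0.33/0.18 |
| Slope-only code, k = 1 | 0.33 each | 0.61/0.33/0.06 |
| Slope-only code, k = 2 | 0.33 each | 0.79/0.33/-0.13 |

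**Effect on the estimate** (weights times visit effects, in units of the Week 12 SD for the unstructured cases). For a growing effect 0.30/0.45/0.60 with SDs 0.8/1.0/1.2, the addendum gives 0.77×0.30 + 0.24×0.45 − 0.01×0.60 = 0.231 + 0.108 − 0.006 = 0.33. V3.0 gives 0.45.

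| Case | V3.0 | Addendum, growing | Addendum, waning 0.60/0.45/0.30 |
|---|---|---|---|
| Equal SDs | 0.45 | 0.45 | 0.45 |
| SD 0.9/1.0/1.1 | 0.45 | 0.39 | 0.51 |
| SD 0.8/1.0/1.2 | 0.45 | 0.33 | 0.57 |
| Slope-only, k = 1 | 0.45 | 0.37 | 0.53 |

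A constant effect does not move in any case.

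**Error rate and power.** REML simulation with unstructured V estimated: 80 per arm, 5% lost after Week 8 and 5% after Week 12, t test with 152 df in place of Kenward-Roger, LSMEANS at mean time (8 + 0.95×12 + 0.90×16)/2.85 = 33.8/2.85 = 11.86. There were 3000 to 4000 null runs per case (Monte Carlo SE 0.3 to 0.4 points) and 700 or 1000 runs per alternative.

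| Case | Type I error, V3.0 / addendum | At least one significant, null | Power, growing, V3.0 / addendum | Power, waning, V3.0 / addendum |
|---|---|---|---|---|
| CS 0.6, equal SDs | 5.1 / 5.2% | 5.4% | 88 / 87% | 90 / 90% |
| AR 0.7, equal SDs | 5.1 / 5.2% | 5.4% | not run | not run |
| SD 0.9/1.0/1.1 | 4.5 / 4.8% | 5.8% | 88 / 80% | 89 / 95% |
| SD 0.8/1.0/1.2 | 4.7 / 5.0% | 7.0% | 88 / 75% | 89 / 99.6% |

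Analytic check of the third column: the two test statistics correlate at SE(addendum)/SE(V3.0) = 1.000, 1.000, 0.973 and 0.903. A bivariate normal then gives 5.1, 5.1, 6.1 and 7.0%.

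A separate simulation of the slope-only code, with other assumed variances, points the same way. An effect growing from -0.15 to -0.45 was estimated at -0.28 with the interaction and -0.18 without. One fading from -0.45 to -0.15 gave -0.31 and -0.40. With a constant effect of -0.3, the two models disagreed on significance in 13% of trials.

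**The case against.** The sponsor used the route that Section 5 provides and stated the timing openly, so no SAP rule is plainly broken. That stands. The fault is the missing reason and status, and nothing is concealed.

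The original-text/new-text layout suggests that the addendum model simply is the primary analysis, so the gate is not really open. That is the more natural reading, and the at-least-one figures apply only if it is wrong. But it makes a model chosen after unblinding the gate, which is the more serious of the two outcomes.

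The numerical harm is conditional. Each model alone holds about 5% under the stated unstructured covariance. The large shifts need both SDs that change over visits and an effect that varies by visit, and the SAP supplies neither. This also stands, and the figures show only that the change can matter. The no-change cases are specific too: equal SDs with unequal correlations (0.5/0.4/0.7) still move the growing effect slightly, from 0.45 to 0.44.

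V3.0 itself is not perfectly unique. Its text and example code differ on covariance, and Section 2.3 omits age where Section 5.10.2.1 includes it. TUG and NTB change only by cross-reference, and NTB also has a Week 4 visit in the early-withdrawal mapping, so the three-visit weights do not carry over to it. These are fair limits on size and reach and do not answer the main point. A few addendum pages were not in the text available, so statements about what it omits cover only what is shown.

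**Conclusion.** The concern holds, and the plan is wrong as written on this point. An unexplained replacement of the primary, sensitivity and, by reference, TUG and NTB models was made after unblinding. The p-value that drives Section 5.10.5 is not tied to the prespecified model. This follows from the text alone.

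The size depends on assumed covariances and effect shapes. It runs from no shift (equal SDs with CS or AR correlation, a random subject intercept, or a constant effect) to a primary estimate of 0.33 or 0.57 in place of 0.45 at SDs of 0.8/1.0/1.2. If the choice of gate stays open, the upper bound on type I error is about 5.4% to 7.0% in the cases simulated. These figures read the Section 2.3 average as the plain mean of the three visits. The SAP states no weights, and under AR 0.7 V3.0 does not weight the visits equally either. The document has no results, so it does not show which model is more favourable or why the change was made.

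**What to change.** 1. Keep the V3.0 treatment-by-time model as the confirmatory analysis for CDR-SB, its MNAR sensitivity analysis, TUG and NTB. Add one sentence stating that Section 5.10.5 is driven by the p-values from this model alone for CDR-SB, TUG and NTB. ADCS-CGIC keeps its rank test.
2. Report the no-interaction models as post hoc, outside the hierarchy, in their own full-mITT tables next to the V3.0 results, and give the reason for the change.
3. Align the example SAS code with the unstructured within-subject covariance that Section 5.10.2.1 states, documented as a correction to match prespecified text. Reproduce the full covariate list there, so that the age difference from Section 2.3 is settled openly. The code/text conflict was already in V3.0 and is separate from this finding, but it has to be settled for the restored model to be unique.
4. If an explicit equal-weight mean of the Week 8, 12 and 16 differences is also shown, label it a clarification made after unblinding, because V3.0 fixes only a plain LSMEANS statement.

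The cost is addendum wording, one sentence on Section 5.10.5, added or relabelled tables, the code alignment and a rerun of the affected models. No new data are needed.

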### 5.10.2.3 Subgroup Analysis

The change from baseline in CDR-SB will be analyzed in for each subgroup of cholinesterase inhibitor therapy (Yes / No) separately, using similar methods as described in Section [5.10.2.1](#) except cholinesterase inhibitor therapy covariate will be removed from the model.

QMD Ref: Worldwide-TMP-ST-054-1.0 Effective: 12Aug2022	Governing QMD: Worldwide-SOP-ST-026
Confidentiality Statement	

This document is the property of Worldwide Clinical Trials Inc. and may not be duplicated, copied, altered or removed from company without prior approval from Worldwide Quality Assurance or in compliance with Worldwide Standard Operating Procedures.

Worldwide Clinical Trials Controlled Quality Management Document		
 WORLDWIDE CLINICAL TRIALS	Sponsor:	EIP Pharma, Inc.
	Protocol Number:	EIP21-NFD-504
STATISTICAL ANALYSIS PLAN		

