**POST DATABASE LOCK STATISTICAL ANALYSIS PLAN ADDENDUM**

Table Number	Table Title	Validation Method	Shell Number (if repeat)
	Model), pTau181 <21 at Screening - Double-Blind Treatment Phase – mITT Analysis Set		
14.2.2	Secondary Efficacy Endpoints		
14.2.2.1.1c	Secondary Endpoint, Change in Timed Up and Go Test (Descriptive Statistics), pTau181 <21 at Screening - Double-Blind Treatment Phase - mITT Analysis Set	Stat IP	14.2.2.1.1a
14.2.2.1.2b	Secondary Endpoint, Change in Timed Up and Go Test (Linear Mixed Effects Model), pTau181 <21 at Screening - Double-Blind Treatment Phase - mITT Analysis Set	Stat IP	14.2.2.1.2
14.2.2.2.2c	Secondary Endpoint, Composite Score of Neuropsychological Test Battery (Descriptive Statistic), pTau181 <21 at Screening - Double-Blind Treatment Phase – mITT Analysis Set	Stat IP	14.2.2.2.2a
14.2.2.2.3b	Secondary Endpoint, Composite Score of Neuropsychological Test Battery (Linear Mixed Effects Model), pTau181 <21 at Screening - Double-Blind Treatment Phase - mITT Analysis Set	Stat IP	14.2.2.2.3
14.2.2.3.1c	Secondary Endpoint, Alzheimer's Disease Cooperative Study Clinical Global Impression of Change (Descriptive Statistics), pTau181 <21 at Screening - Double-Blind Treatment Phase - mITT Analysis Set	Stat IP	14.2.2.3.1a
14.2.2.3.2b	Secondary Endpoint, Alzheimer's Disease Cooperative Study Clinical Global Impression of Change (Mann Whitney U Test), pTau181 <21 at Screening - Double-Blind Treatment Phase - mITT Analysis Set	Stat IP	14.2.2.3.2

QMD Ref: Worldwide-TMP-ST-056-2.0\_Effective: 12Aug2025

Governing QMD: Worldwide-SOP-ST-026

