## **Approach for OLE Analysis**

### **Treatment groups:**

There are five treatment groups in the OLE:

Group 1 = old batch for all of OLE (or through ET), N=20

Group 2 = started OLE on old batch, switched at W16 OLE, N=35

Group 3 = started OLE on old batch, switched at W8 OLE, N=26

Group 4 = started OLE on old batch, switched at W4 OLE, N=22

Group 5 = new batch for all of OLE (or through ET), N=46

Total=149, though not all the participants above will be in the mITT analysis, with some being excluded because they do not have at least one efficacy evaluation during the OLE.

In addition, three populations will be evaluated:

1. All participants in OLE
2. OLE participants with screening plasma ptau181 <25.2 pg/mL (2.2 pg/mL in prior version of assay)
3. OLE participants with screening plasma ptau181 < 21 pg/mL (1.8 pg/mL in prior version of assay)

For OLE week 8 data point, groups 1, 2 and 3 will be pooled under “old capsule treatment” and only group 5 will be included under “new capsule treatment” (i.e. only participants with  $\geq 8$  weeks of new capsules will be included).

For the week 16 OLE analysis, groups 1 and 2 will be pooled under the label of “Old Capsules Treatment”, and groups 3, 4 and 5 will be pooled under the label of “New Capsule Treatment” (i.e. all participants with  $\geq 8$  weeks of new capsules will be included for the new capsule treatment group).

The baseline value for all change analyses will be the value at the end of the double-blind period, i.e. at week 16 of the main study (if no value, week 12 will be carried forward).

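### The post-unblinding addendum reports efficacy only for pTau181 below 21, with no complement and no interaction estimate, so its tables cannot separate a pTau181-specific effect from a common one

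*SAP*

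**What the plan says.** The addendum's Background section dates itself plainly: "These amendments were made post database lock and after the study was unblinded". Its third reason is "Additional tables generated to report the efficacy analysis for subjects with pTau181 <21 pg/mL at Screening".

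Section 3.2 of the addendum introduces the list with "Following additional tables are added to the analysis". Eight tables follow. For each of CDR-SB, TUG, NTB composite and ADCS-CGIC there is one descriptive and one inferential table: a linear mixed effects model for the first three and a Mann-Whitney test for ADCS-CGIC. Every title carries the same restriction, for example "Secondary Endpoint, Change in Timed Up and Go Test (Linear Mixed Effects Model), pTau181 <21 at Screening". No title refers to subjects at or above 21, and none to an interaction.

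The revised primary model in addendum section 2.2.2 has treatment and time as fixed effects, with "cholinesterase inhibitor therapy (Yes/No), age, sex and baseline value as covariates". The revised code in sections 2.3 and 2.4 matches. pTau181 appears in neither.

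SAP v3.0 plans one treatment-effect subgroup factor, and there it analyses CDR-SB "for each subgroup of cholinesterase inhibitor therapy (Yes / No) separately" (section 5.10.2.3). Sections 5.10.3.1 to 5.10.3.3 do the same for the three secondary endpoints.

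The separate approach for the open-label extension (OLE) uses three nested populations: all participants, "OLE participants with screening plasma ptau181 <25.2 pg/mL", and those below 21. It gives the earlier-assay equivalent of 21 as 1.8 pg/mL.

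**The concern.** A table restricted to one side of a biomarker cut-off answers one question: what was the treatment difference in those subjects? It does not answer whether the difference depends on the biomarker. That needs the other side and a contrast between the two, and the addendum plans neither.

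A favourable result below 21 would fit an effect confined to those subjects, a common effect in everyone, or chance. If it were used to describe who responds, or to select patients for a later trial, the report would hold no estimate to support or contradict that use. The plan already shows the better layout in its cholinesterase inhibitor subgroup, where both levels are reported.

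Timing adds to this. In subgroup tables added after unblinding, a reader needs to know where the cut-off came from, and the visible addendum text gives neither its source nor its date.

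**Working it through.** **Reading check.** All eight added titles name pTau181 below 21. Titles for 21 and above: none. Interaction tables: none. Model terms involving pTau181 in the revised text and code: none.

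**Inputs**
- 80 subjects per arm, 1:1, and 10% dropout (SAP section 3): 80 × 0.90 = 72 evaluable per arm.
- Phase 2a patients without Alzheimer's co-pathology (SAP section 3): difference −0.56 CDR-SB points, Cohen's d = 0.70. Implied SD = 0.56 / 0.70 = 0.80.
- Two-sided alpha 0.05 (SAP section 5.10.1).
- Share f of subjects below 21: not in the document. Assumed 50%, 65% and 80%.

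**The plan's own figure.** SAP section 3 states power greater than 95% for that phase 2a effect. A two-sample calculation with difference 0.56 and SD 0.80 gives 98.7% at 72 per arm and 99.3% at 80 per arm. Both agree with the stated bound, so these inputs are usable for illustration.

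**What the one-sided table can show.** With n_s = 72f per arm below 21 and n_c = 72(1 − f) per arm at or above it, in SD units:

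- SE below 21 = √(2/n_s)
- P(p<0.05 below 21) ≈ Φ(d_below / SE − 1.96)

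The effect above 21 does not enter the formula.

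| Share below 21 | SE below 21 | P(p<0.05), d = 0.70 in everyone | P(p<0.05), d = 0.70 below and 0 above | P(p<0.05), d = 0.50 in everyone |
|---|---|---|---|---|
| 50% | 0.236 | 84% | 84% | 56% |
| 65% | 0.207 | 92% | 92% | 68% |
| 80% | 0.186 | 96% | 96% | 77% |

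The third and fourth columns are identical, so the planned table looks the same in both situations.

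**What the missing contrast would give.** SE of the interaction = √(2/n_s + 2/n_c). The half-width of its 95% CI in CDR-SB points is 1.96 × SE × 0.80.

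| Share below 21 | SE of interaction | Ratio to SE of overall effect | 95% CI half-width | Power, 0.70 below and 0 above | Power, 0.70 below and 0.35 above |
|---|---|---|---|---|---|
| 50% | 0.333 | 2.0 | ±0.52 | 56% | 18% |
| 65% | 0.349 | 2.1 | ±0.55 | 52% | 17% |
| 80% | 0.417 | 2.5 | ±0.65 | 39% | 13% |

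Example at 50%: n_s = n_c = 36, SE = √(2/36 + 2/36) = 0.333, and 1.96 × 0.333 × 0.80 = 0.52. The interval is about as wide on each side as the phase 2a effect of 0.56 itself.

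These are normal approximations for a single summary per subject, not the planned mixed model. They show the order of size.

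**The case against.** The case for leaving the addendum alone has several parts.

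- **No differential claim is made.** This is correct. The addendum says only that it reports efficacy in these subjects. The point is about what the tables could support, not about a claim already made.
- **The additions are disclosed and outside the testing hierarchy.** SAP section 5 provides for a post-lock addendum, the addendum states its timing, and section 5.10.5 does not cover these tables. This stands, and it limits the harm. It supplies neither a complement nor a contrast.
- **The cholinesterase inhibitor subgroup has no interaction test either, and section 5.10.4.3.2 analyses hallucinations only in subjects who report them at baseline.** Both are true. The missing complement is therefore the sharper departure from the plan's own practice. The hallucination restriction explains itself, because it selects those with the symptom at baseline; the cut-off of 21 is not explained.
- **The rest can be worked out from the full mITT tables.** Descriptive means for 21 and above could be approximated by subtraction. A model estimate with its CI, or an interaction, is not planned anywhere in the visible text.
- **The interaction would be imprecise.** It would, as shown in the working. That is a reason to show the interval and make no significance claim.
- **Section 5.11 leaves plasma biomarker analysis to a separate plan that is not shown.** A complementary analysis could be there. If so, the addendum should point to it.

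Three stronger readings are tempting, and the document does not support them. A reader might infer that 21 was picked with the results known. The addendum dates itself, not the cut-off, and the earlier-assay equivalent in the OLE approach leaves room for a prior origin without proving one. A reader might treat 25.2 as a second look at the double-blind data, but it appears only as an OLE population. A reader might put the size of the problem at 1 − 0.95⁴ = 18.5%, the chance of at least one p<0.05 among the four added tests. That is a multiplicity ceiling under independence, for endpoints measured in the same subjects, and it does not measure the missing contrast.

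**Conclusion.** The point holds as a reporting defect. Eight tables added after unblinding describe one side of a pTau181 cut-off, and nothing in the visible text gives the other side or the difference between the two. On the assumed splits, a table below 21 has the same 84% to 96% chance of p<0.05 whether an effect of 0.70 is common to all or confined to that subgroup. It therefore carries no information on effect modification.

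The full-mITT result and the formal error control are not touched by this point. The probabilities and interval widths rest on an assumed 50% to 80% of subjects below 21, 72 evaluable per arm and an SD of 0.80 from phase 2a patients without Alzheimer's co-pathology. The document does not say that pTau181 below 21 defines that group, so the SD and the effect size are illustrative. The conclusion that the tables lack a contrast needs none of these assumptions. Some pages of the addendum were not available, so statements about what is absent refer to the visible text.

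**What to change.** - Add tables for pTau181 at or above 21 matching the eight already listed, shown beside those below 21.
- In the full mITT set, fit treatment-by-pTau181 for CDR-SB, TUG and NTB composite, dichotomised at 21 and, as support, continuous. Report the interaction estimate with its 95% CI.
- For ADCS-CGIC, which is compared by a rank test, show both levels side by side.
- State where the cut-off of 21 came from and whether it was set before unblinding, with the date.
- Label all of these outputs post hoc and exploratory, with no significance claims. Add a sentence that a non-significant interaction is not evidence of an equal effect, given an expected interval of roughly ±0.5 to 0.65 CDR-SB points.

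The cost is a few extra model runs and tables on data already held. The drawback is an imprecise interaction estimate, which the label and the interval make plain.
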